- HCP Checklist for the risks of phototoxicity, SCC of the skin and hepatic toxicity: This is the core RM tool that reminds HCPs about: i) the risks of phototoxicity, SCC of the skin, and hepatic toxicity with the use of voriconazole, ii) the appropriate use of voriconazole and management of patients with underlying hepatic impairment and those developing hepatic injury during voriconazole therapy as described in the SPC, iii) the dermatological examination and liver function monitoring required per the SPC, iv) discussing the importance of monitoring these risks with patients, and, v) providing the Patient Alert Card (described below) to each patient prescribed voriconazole. The HCPs have been instructed to complete the HCP Checklist for all new patients receiving voriconazole and retain it in the patient's medical record.
- HCP Q&A Brochure for the risks of phototoxicity, SCC of the skin and hepatic toxicity: This brochure in Q&A format provides detailed information to HCPs about: i) the risks of phototoxicity, ii) counselling patients regarding the risks of hepatotoxicity and SCC of the skin, iii) alerting patients/caregivers to the signs and symptoms that warrant contacting the doctor immediately, iv) regular dermatological examination and liver function monitoring as described in the SPC, v) discontinuing voriconazole if premalignant lesions or SCC are identified; and, vi) providing the Patient Alert Card to patients prescribed voriconazole. This brochure also provides information about the HCP Checklist and Patient Alert Card and instructs HCPs how to use these tools when managing patients receiving voriconazole.
- Patient Alert Card for the risks of phototoxicity and SCC of the skin: The purpose of this wallet-sized folded card is to help remind patients about the need for dermatological evaluations on a regular basis (if phototoxic reactions occur). It also prompts the patient to report phototoxic symptoms that increase the risk of SCC of the skin. Furthermore, patients are reminded to avoid exposure to sunlight, to use protective clothing and sunscreen with high sun protective factor (SPF), and to inform their physicians if they develop sunburn or severe skin reactions or skin abnormalities. The HCPs were instructed to fill in their contact details on the card and give a card to each patient undergoing treatment with voriconazole.

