9.1.1. Endpoints

- 1 The proportion of targeted HCPs who acknowledge receiving each of the RM tools.
- 2 The proportion of targeted HCPs who acknowledge reading and utilizing the tools.
- 3 The proportion of targeted HCPs who responds to correctly to questions about the risks of phototoxicity, SCC of the skin, and hepatic toxicity.
- 4 The proportion of targeted HCPs who provided desirable responses to the practicerelated questions and self-declared behavior with regard to strategies to mitigate the risks.

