Phototoxicity (eg, skin rash)			
Intestinal perforation			
Squamous cell carcinoma (SCC) of the skin			
Asthma			
Hepatic toxicity			
Cardiomyopathy			

8. Please select only one response for each statement about VFEND (voriconazole) below:

	True	False	I Don't Know
Long-term treatment (>6 months) with VFEND (voriconazole) should be considered only if the benefits outweigh the potential risks			
If phototoxic reactions occur, multidisciplinary advice should be sought and the patient should be referred to a dermatologist			
VFEND (voriconazole) should not be discontinued if premalignant skin lesions or skin Squamous Cell Carcinoma are identified			
Laboratory evaluation of hepatic function (specifically AST and ALT) at initiation and during the first month of treatment with VFEND (voriconazole) is not necessary			
If the Liver Function Tests become markedly elevated, VFEND (voriconazole) should be discontinued , unless the medical judgment of the risk-benefit balance of the treatment for the patient justifies continued use			

9.		you or your hospital receive the VFEND (voriconazole) Healthcare Professional P) Q&A Brochure?
		Yes
		No [GO TO Q10]
		I don't remember receiving it [GO TO Q10]
DISP	LAY '	THE FOLLOWING IMAGE ON THE SAME PAGE NEXT TO Q9]
		VFEND®(Voriconazole) Oral/Intravenous Healthcare Professional Question & Answer Brochure
		NFIDENTIAL Version 2, December 2022 SAU-0064 Page 2
9.1.	Did :	you read the VFEND (voriconazole) HCP Q&A Brochure ?
		Yes, all of it
		Yes, some of it
		No, I did not read it
		I don't remember reading it
		Redacted

Page 39 of 53

Voriconazole A1501110 NON-INTERVENTIONAL STUDY PROTOCOL Version 1.0, 16 August 2024

10.	Did you or your hospital receive copies of the VFEND (voriconazole) Healthcare
	Professional (HCP) Checklist?

Yes
No [GO TO Q11]
I don't remember receiving it [GO TO Q11]

|DISPLAY THE FOLLOWING IMAGE ON THE SAME PAGE NEXT TO Q10

VFEND® (Voriconazole) Healthcare Professional Checklist

Please complete this Checklist at each visit with your patient being treated with VFEND® (Voriconazole). Each of the three sections includes important risk information followed by a series of check boxes to help in the management of your patient for whom you prescribed VFEND.

A) Minimizing the Risk of Phototoxicity and Skin Squamous Cell Carcinoma

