Annex 1.5. Assessment of success

Objectives	Questions	Is the question included in the assessment of success? (Yes/No)	Definition of desirably/correctly answered question	Assessment of success
Awareness of the RM tools	Q9. Did you or your hospital receive the VFEND (voriconazole) Healthcare Professional (HCP) Q&A Brochure?	Yes	Question completed desirably (Answer 1 is desirable)	An HCP is considered successful for awareness when he/she
	Q10. Did you or your hospital receive copies of the VFEND (voriconazole) Healthcare Professional (HCP) Checklist?	Yes	Question completed desirably (Answer 1 is desirable)	acknowledges receiving all RM tools Success for awareness: if
	Q11. Did you or your hospital receive copies of the VFEND (voriconazole) Patient Alert Card?	Yes	Question completed desirably (Answer 1 is desirable)	≥80% of HCPs are successful
	Q12. Did you or another staff member obtain the VFEND (voriconazole) RM tools by downloading them from a website?	No	Complementary question	
Reading and Utilizing the tools.	Q9.1 Did you read the VFEND (voriconazole) HCP Q&A Brochure?	Yes	Question completed desirably (Answers 1 & 2 are desirable)	An HCP is considered successful for utilization when
	Q10.1 Did you read the VFEND (voriconazole) Healthcare Professional (HCP) Checklist?	Yes	Question completed desirably (Answers 1 & 2 are desirable)	he/she reports reading all/some of all RM tools and
	Q11.1 Did you read the VFEND (voriconazole) Patient Alert Card?	Yes	Question completed desirably (Answers 1 & 2 are desirable)	always/sometim es using them Success for
	Q14. When treating patients with VFEND (voriconazole) in the past 12 months, how often did you use the VFEND HCP Checklist?	Yes	Question completed desirably (Answers 1 & 2 are desirable)	utilization: if ≥80% of HCPs are successful
	Q15. When treating patients with VFEND (voriconazole) in the past 12 months, how often did you use the HCP Q&A Brochure?	Yes	Question completed desirably (Answers 1 & 2 are desirable)	

	Q16. When treating patients with VFEND (voriconazole) in the past 12 months, how often did you distribute and fill in the Patient Alert Card? Q17. Did you find the VFEND (voriconazole) RM tools to be of use in your clinical practice? Please select only one rank for each RM tool (Q17.1, Q17.2 and Q17.3)	Yes No	Question completed desirably (Answers 1 & 2 are desirable) Complementary question	

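### Q14 asks how often the HCP used the Checklist without saying what use means, so consulting the form without completing it can score as desirable

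*Protocol*

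**What the plan says.** Section 7 of the protocol introduces the Checklist with "This is the core RM tool that reminds HCPs about" and then lists what it reminds HCPs of. It goes on: "The HCPs have been instructed to complete the HCP Checklist for all new patients receiving voriconazole and retain it in the patient's medical record". The Checklist displayed beside Q10 in Annex 1.2 carries its own instruction: "Please complete this Checklist at each visit with your patient being treated with VFEND® (Voriconazole".

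Section 9.1.1 gives the second endpoint as "The proportion of targeted HCPs who acknowledge reading and utilizing the tools". For the Checklist, the utilization item in Annexes 1.2 and 1.5 is Q14: "how often did you use the VFEND HCP Checklist", answered *Always*, *Sometimes* or *Never*. Annex 1.5 scores it as "Question completed desirably (Answers 1 & 2 are desirable", so only *Never* fails. The matching item for the Patient Alert Card is Q16: "how often did you distribute and fill in the Patient Alert Card".

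An HCP succeeds on utilization in Annex 1.5 by having read all or some of every tool (Q9.1, Q10.1, Q11.1) and by using each at least sometimes (Q14, Q15, Q16). The programme succeeds on this objective if at least 80% of HCPs do.

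**The concern.** The Checklist is a form with boxes to tick for each patient. The programme told HCPs what to do with it, but Q14 does not ask whether they did it. A respondent may take *use* to mean completing the form, or looking at it as a reminder, and both give the same scored answer.

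Objective 2 contributes to the judgement on whether the measures work. If *use* covers consulting, a favourable Q14 result does not show that the core tool was completed, and the report could be read as if it did. Moving the frequency cut-off would not cure this, because the act itself is not asked about.

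**Working it through.** The plan has no figure on this point to reproduce; the sample of 10 is described as empirical. The check is of the text, followed by an illustration.

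**1. Instruction against item, tool by tool**

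| Tool | Instruction in Section 7 | Utilization item | Instructed act named? |
|---|---|---|---|
| Checklist | complete, and keep in the record | Q14: use | No |
| Patient Alert Card | add contact details, give to each patient | Q16: hand out and fill in | Yes |
| Q&A Brochure | none comparable (information to read) | Q15: use | Not applicable |

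**2. Is completion asked about elsewhere?** The items on the Checklist are Q10 (receipt), Q10.1 (reading), Q14 (use) and Q17.2 (usefulness, complementary and unscored). Q12 and Q23 concern downloading and requesting the tools in general. Q18a lists activities at treatment initiation, and completing the Checklist is not among them. No item covers completion or filing.

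**3. What Q14 adds to Q10.1.** The composite already requires that the Checklist was read in whole or part. If *use* is taken as consulting, Q14 adds only how often that happened. It separates a completer from a reader only if the respondent takes *use* to mean *complete*.

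**4. Direction.** All six items must be desirable. A non-completer who answers *Always* or *Sometimes* can only raise the number of successful HCPs. The opposite error, a completer who answers *Never*, is unlikely. The error therefore runs mainly upward.

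**5. Can it be recovered later?** Section 9.6 rules out queries to respondents, Section 9.9.1 says earlier answers cannot be edited, and Section 11 says no individual-patient data are collected. An SAP cannot reconstruct an act that was not asked about.

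**6. Illustration, Q14 alone, with assumed rates.** Let *c* be the true share of HCPs who complete the Checklist at least sometimes, and *m* the share of the others who still report using it. Assume that completers all report use and that respondents are independent. The apparent rate is a = c + (1 − c)m. With 10 completed surveys, 80% means at least 8, so

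P(X ≥ 8) = Σ C(10,k) a^k (1 − a)^(10−k), k = 8, 9, 10.

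For c = 0.5 and m = 0.5, a = 0.5 + 0.5 × 0.5 = 0.75, and P = 0.526. With m = 0, a = 0.5 and P = (45 + 10 + 1)/1024 = 0.055.

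| c | m = 0 | m = 0.25 | m = 0.5 | m = 0.75 | m = 1 |
|---|---|---|---|---|---|
| 0.3 | 0.002 | 0.039 | 0.262 | 0.752 | 1.0 |
| 0.5 | 0.055 | 0.211 | 0.526 | 0.880 | 1.0 |
| 0.7 | 0.383 | 0.602 | 0.820 | 0.966 | 1.0 |

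The documents give neither *c* nor *m*. The table shows how strongly the Q14 result could depend on how *use* is read. It does not say how large the effect will be, and it does not describe the six-item composite.

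**The case against.** The best defence is that Q14 does what the protocol promises. The objective speaks of utilization, the endpoint of utilizing the tools, and Section 9.3 of how often they are used. None of them promises to measure completion or filing. Section 7 first describes the Checklist by what it reminds HCPs of, so consulting it is arguably one of its purposes. The form is displayed at Q10 with its instruction to complete it, so many respondents will read *use* as *complete*. The Card is held by the patient, which makes naming the act more necessary in Q16 than in Q14. The practices that the Checklist prompts are scored separately in Q18 to Q22.

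Much of this stands, and it rules out some stronger readings that a reader might infer:

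- That Section 7 defines use as completing and filing. It does not. Those acts are a separate instruction that follows the description of the tool.
- That an HCP who never completes a Checklist is thereby a full user. Q14 is one of six items; the HCP must also have read all three tools, used the Brochure, and filled in and handed out Cards.
- That merely having the form on the ward would count. Q14 asks what the respondent did when treating patients.
- That the survey would show full use where there is none. All 10 respondents consulting and none completing is arithmetically possible, but nothing in the documents makes it likely.

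The defence does not remove the ambiguity. The display at Q10 may guide some respondents, but the item and its scoring leave *use* open. Q18 to Q22 measure practice, which an HCP may follow with or without the form.

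**Conclusion.** The point holds as one of item wording. Q14 does not distinguish completing the Checklist from consulting it, no other item does, and both can score as desirable on one of the six utilization items. Misclassification is possible rather than certain, and mainly upward. Its size cannot be estimated, because it depends on how respondents read *use* and on how many complete the form; the documents give neither. The conclusion rests only on the wording and scoring fixed in Annexes 1.2 and 1.5 and on the instruction in Section 7. It is worth correcting because the gap cannot be closed at analysis and is cheap to close now.

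A related inconsistency needs attention first. Section 7 ties completion to all new patients, while the displayed Checklist ties it to each visit. Until these are reconciled, *Always* has no agreed denominator.

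**What to change.** - **Q14, Annexes 1.2 and 1.5:** ask how often, when treating patients with voriconazole in the past 12 months, the HCP completed the VFEND HCP Checklist. Keep the three response options, score this item, and align the description of utilization success in Annex 1.5 with it.
- **Retention:** ask about filing in the medical record in a separate item, for example a complementary one, and add it to the list in Section 9.4. A single question on completing and filing would leave an HCP who does one but not the other without a clear answer.
- **Unit:** keep the question to the individual HCP, on whom the success rule is defined. Do not extend it to the team.
- **Reconcile** Section 7 with the displayed Checklist on when it is to be completed, before the item is finalised.

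The cost is one or two items changed before the survey is programmed. Reported utilization may be less favourable, but it will be clear what it means.

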9.9. Strengths and Limitations of the Research Methods

9.9.1. Strengths

1. Web-based surveys

Redacted

Web-based surveys have been selected as the preferred research approach because:

- The HCP survey includes behavioral scenario-based questions that might be difficult to implement using other approaches.
- Web-based surveys can be answered at the participant's convenience so that an interview does not need arranging this can increase a participant's motivation to do the survey (improving response rates), thus resulting in more consistent completion of surveys.
- Web-based surveys are programmed to ask standardized questions and should elicit more consistent and reliable results than questions asked by telephone interviewers.
- Web-based techniques allow for a degree of interactivity to be introduced into the survey (e.g., logic to ask follow-on questions or not ask irrelevant questions), which strengthens the validity of the behavioral scenarios.
- 2. Questionnaire design and testing
- The web questionnaires include general questions followed by specific ones. They include both open and closed questions. As the HCPs may understand the right answer in subsequent questions, it will not be possible to go back in the questionnaire and edit answers in former questions.
- The questionnaires will be tested for their clarity. It will also be checked whether there are questions which would suggest a specific answer for any reason.
- 3. Experience in drug safety and the evaluation of RM measures

The study will be conducted by an experienced team specialized in the design and conduct of such surveys. It follows SOPs, as well as the methodological guidelines from SFDA Guideline on GVP.

4. Quality control and compliance

Quality controls are implemented on a regular basis by our teams.

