Not useful 17.2 HCP Checklist rograming Note: if response to Q11 or (Not Som useful us 17.3 Patient Alert	Somewhat useful Q12 is YES, the newhat	No opinion/not sure 	Very useful	Extremely useful
useful 17.2 HCP Checklist rograming Note: if response to Q11 or Q Not Som useful us 17.3 Patient Alert	useful Q12 is YES, the newhat	opinion/not sure	useful	useful
rograming Note: if response to Q11 or	Q12 is YES, the	hey can continu		
Not Som useful us	iewhat]		ie with Q	17.3
useful us 17.3 Patient Alert		NI. X7		
	-	No Ver nion/not usef sure	•	remely seful
Which precautionary measures d prescribe VFEND (voriconazole))? Please check			or whom you
Avoiding exposure to dire		taviaity		
Detecting signs and symptUse with caution in patien	•	•	testinal u	lceration or
diverticulitis	•	•		
Dermatologic evaluation s basis	hould be perfo	formed on a syst	tematic ar	nd regular

	Covering sun exposed areas of skin		
	Use sufficient sunscreen with high sun protect	ion factor (SPF)	
	Clinical signs of liver damage, such as jaundic doctor immediately	e that warrant con	tacting the
	International Normalized Ratio regular monitor	oring	
	Avoid invasive dental procedures		
	Note: if response to Q11 or Q12 is YES, they can tents of the Patient Alert Card" in Q18a	n continue with op	otions
18a.	Do you, or another member of your healthcar other) perform each of these activities when it VFEND (voriconazole)? (Please check one rebelow).	nitiating treatment	with
		Yes	No
	Discuss contents of the Patient Alert Card		
	Advise patient to avoid exposure to direct sunlight and/or to use measures such as protective clothing and sunscreen		
	Discuss risk of lymphoma		
	Discuss risk of gastric perforation		
	Advise patient of importance of monitoring risks of VFEND (voriconazole) use and signs and symptoms of serious risks that warrant contacting doctor immediately		
	Discuss risk of amyloidosis		
19. How	frequently do you perform Liver Function Tests	s (specifically AST	T, ALT)?
	At VFEND (voriconazole) treatment initiation month	and weekly therea	after for one
	At every contact		
	Monthly		

		Other [Free text] I do not know
20.	of VI	ere are no changes in Liver Function Tests (LFTs) after one month of initiation FEND (voriconazole), how often do you monitor liver function during VFEND ment maintenance?
		Weekly
		Monthly
		Other [Free text]
		I do not know

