Knowledge about the RM tools	Q7. According to the SPC/PI, the known risks for VFEND (voriconazole) are as follows: (Please select only one response for each of the risks listed in the table below.) Q8. Please select only one response for each statement about VFEND	Yes	Question completed correctly (6 points) Question completed correctly (5 points)	An HCP is considered successful for Knowledge when he/she provides at least 9 out of 11 (~80%) correct/desirable responses. Success for
Self-declared behavior/ Practice	(voriconazole) below: Q18. Which precautionary measures do you communicate to your patients for whom you	Yes	Question completed desirably (6 points)	Knowledge: if ≥80% of HCPs are successful An HCP is considered successful for awareness when he/she provides
	prescribe VFEND (voriconazole)? Please check all that apply. 18.a Do you, or another member of your healthcare team (e.g., nurse, pharmacist or other) perform each of these activities when initiating treatment with VFEND (voriconazole)? (Please check one response for each activity below).	Yes	Question completed desirably (6 points)	desirable responses to all sub-questions. Success for self-reported practices if ≥80% of HCPs are successful
	Q19. How frequently do you perform Liver Function Tests (specifically AST, ALT)?	Yes	Question completed desirably (Answer 1 is desirable)	

Q20. If there are no changes in Liver Function Tests (LFTs) after one month of initiation of VFEND (voriconazole), how often do you monitor liver function during VFEND treatment maintenance?	Yes	Question completed desirably (Answer 2 is desirable)	
Q21. How often do you perform a dermatologic evaluation when VFEND (voriconazole) is continuously used despite the occurrence of phototoxicity related lesions?	Yes	Question completed desirably (Answer 4 is desirable)	
Q22. For which of below condition(s) would you discontinue VFEND (voriconazole) in a patient? (Select the one best response).	Yes	Question completed desirably (Answer 4 is desirable)	

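### The liver-test question Q19 names no treatment phase, so an HCP who follows the keyed schedule could answer Monthly and be scored a practice failure (minor)

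*Protocol*

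**What the plan says.** The practice part of the Protocol's Annex 1.5 scores two liver-monitoring questions.

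- **Q19** reads "Q19. How frequently do you perform Liver Function Tests (specifically AST, ALT" and names no phase. In Annex 1.2 its options are testing at the start and weekly for a month (the option opening "At VFEND (voriconazole) treatment initiation"), at every contact, Monthly, a free-text Other, and a don't-know option. Only the first is keyed as desirable.
- **Q20** supposes unchanged liver tests after one month and asks "how often do you monitor liver function during VFEND treatment maintenance". Its key is "Question completed desirably (Answer 2 is desirable", which is Monthly.

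An HCP succeeds on practice only with "desirable responses to all sub-questions", and the programme succeeds on this objective if at least 80% of HCPs do. Section 9.9.1 says that "it will not be possible to go back in the questionnaire and edit answers in former questions", and section 9.6 rules out queries to respondents. Section 9.5 aims for 10 completed surveys but makes the final number depend on willingness to take part. It also says the 80% criterion will not be formally tested.

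**The concern.** The two keys describe a single monitoring schedule split across two questions, but only the second question says which part it covers. At Q19 the respondent does not yet know that maintenance will be asked about separately. Someone who tests weekly in month one and monthly afterwards finds no option for the whole schedule. The first option covers month one, and Monthly covers the rest of treatment. If that person answers for the longer phase, the answer is scored as undesirable.

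The result would be a misclassification: an HCP whose practice matches the plan's own key is counted against objective 4. Section 9.7 promises the distribution of answers to each practice question, so a cluster of Monthly answers at Q19 would be visible. The reason for it would not be. A misread stem and sparse early monitoring produce the same tick, on an item meant to measure control of hepatic toxicity.

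**Working it through.** The plan gives no figure on this point to reproduce. The check compares wording with key, then does some counting.

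**1. Wording against key**

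| | Phase in stem | Keyed answer | Is Monthly offered? |
|---|---|---|---|
| Q19 | none | start of treatment, then weekly for one month | yes, not credited |
| Q20 | after month one, maintenance | Monthly | yes, credited |

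An HCP on the combined schedule is described by option 1 at Q19 for the first month and by Monthly for the time after it. Writing the full schedule under Other would also fail as the key stands, because only answer 1 is credited.

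**2. How many such answers matter**

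Successes needed = 0.80 × n, rounded up.

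- n = 10: 8 needed, so 2 failures are tolerated. Three give 7/10 = 70%.
- n = 9: 0.80 × 9 = 7.2, so 8 needed and 1 failure is tolerated. Two give 7/9 = 78%.
- n = 5: 4 needed, so 1 failure is tolerated. Two give 3/5 = 60%.
- n = 6, 7 and 8 also tolerate 1 failure. Two give 4/6 = 67%, 5/7 = 71% and 6/8 = 75%.

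**3. Illustration under assumed misreading rates**

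Let m be the chance that an HCP on the keyed schedule ticks Monthly at Q19, independently between HCPs, with every other practice item desirable. The documents give no value for m. The values below are assumptions.

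| m | P(at least 3 of 10), Binomial(10, m) | P(at least 2 of 9), Binomial(9, m) |
|---|---|---|
| 0.05 | 0.012 | 0.071 |
| 0.10 | 0.070 | 0.225 |
| 0.20 | 0.322 | 0.564 |

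**4. Beside the all-items rule**

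The practice sub-questions number 6 (Q18) + 6 (Q18a) + 4 (Q19 to Q22) = 16, so 15 besides Q19. Suppose each of the 15 is desirable with probability p, independently. The chance that an HCP passes is then p^15 × (1 − m). The chance that at least 8 of 10 pass is:

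| p | p^15 | m = 0 | m = 0.05 | m = 0.10 | m = 0.20 |
|---|---|---|---|---|---|
| 0.99 | 0.860 | 0.846 | 0.729 | 0.599 | 0.352 |
| 0.98 | 0.739 | 0.492 | 0.387 | 0.295 | 0.153 |
| 0.95 | 0.463 | 0.033 | 0.024 | 0.016 | 0.007 |

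These are illustrative too. Items will not be equally hard or independent, and the Patient Alert Card item in Q18a is shown only to HCPs who answered Yes at Q11 or Q12. Unless the other items are answered almost perfectly, the requirement to get all of them right limits success more than Q19 does.

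**The case against.** The strongest reply is that the HCP in question is offered a listed description of their own first month. Option 1 says what they do at the start, whereas Monthly misstates it. There are further cues. Q18a, immediately before, asks whether the team will "perform each of these activities when initiating treatment with VFEND (voriconazole". Q8 has already raised "Laboratory evaluation of hepatic function (specifically AST and ALT) at initiation and during the first month of treatment with VFEND (voriconazole". Section 9.9.1 plans clarity testing, which is where such an ambiguity should be caught. The 80% criterion is descriptive, and section 9.7 will show the answers to each question. All of this stands. It makes the error less likely and partly visible. It does not make Monthly untrue of the later phase, and an answer given in error cannot be repaired after fielding.

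A reader might infer that this wording will materially distort the practice result. The documents do not support that. They give no misreading rate, and at n = 10 two such HCPs still leave 80%.

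A reader might also infer that Q20 is mis-keyed because Weekly, the denser schedule, earns no credit. That does not follow either. Objective 4 asks for accordance with the SPC, not for monitoring at least as frequent, and the SPC is not among the documents. No error in the Q20 key is shown, and no change to it is proposed.

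**Conclusion.** The point holds as a minor wording fault. It is certain that Q19 lacks a phase, that Q20 has one, that Monthly is available but uncredited at Q19, and that one such answer fails the HCP. How often it would happen is unknown. Three cases among 10 completed surveys, or two among 5 to 9, would take practice success below 80% even if every HCP followed the keyed schedule and answered everything else as desired. The probabilities shown rest on assumed rates and independence, and should be read only as a range.

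**What to change.** In Annex 1.2 and Annex 1.5, open the Q19 stem with *During the first month of VFEND treatment,* and leave the rest of the question as it is. The options, the key and the 80% threshold do not change. This matches how Q20 is already drafted.

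The cost is one phrase in two places before programming. With the month named, Monthly becomes a weaker distractor and answer 1 slightly easier to guess. Two limits remain. An HCP who sees patients weekly in month one could still truthfully choose the every-contact option, and the change does nothing about the strictness of requiring every practice item to be desirable.
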